6.2.3.3 Symptomatic Hypocalcemia

The clinical signs and symptoms of hypocalcemia include increased neuromuscular excitability, manifested as paresthesias of the fingers, toes, and circumoral region. In more extreme cases, there may be muscle cramping, carpopedal spasm, laryngospasm, and seizures. Symptoms reflect not only the degree of hypocalcemia, but also the acuteness of the fall in serum calcium concentration. Signs of latent tetany include Chvostek's sign (twitching of the upper lip after tapping on the facial nerve below the zygomatic arch) and Trousseau's sign (carpal spasm after inflating a cuff on the upper arm above systolic blood pressure for 2 to 3 minutes). Various mental disturbances, such as irritability, depression, and even psychosis, have been attributed to hypocalcemia. Cardiac effects of hypocalcemia include a prolonged QT interval and, rarely, ventricular tachyarrhythmia's or congestive heart failure which may be fatal.

Common symptoms of hypocalcemia include paresthesias (fingertips, toes, or perioral), fatigue, muscle cramps, irritability or anxiety, tetany (eg, carpopedal spasm, laryngospasm), Chvostek's sign, seizures, and prolonged QT interval.

If symptomatic hypocalcemia is suspected, calcium levels should be closely monitored, and corrective measures should be undertaken by the Investigator. Calcium supplementation can be provided by IV infusion (eg, a calcium gluconate) and/or oral calcium supplementation.

Suppressed levels of serum magnesium can be associated with refractory hypocalcemia. Serum magnesium should be closely monitored in subjects with hypocalcemia, and magnesium supplements should be provided as needed.

If dosing with IP is suspended for symptomatic hypocalcemia, dosing may resume at a lower dose once symptomatic hypocalcemia has resolved when the central laboratory cCa ≥ 8.3 mg/dL (2.07 mmol/L), and once the Investigator has notified the IVR/IWR.

6.2.3.4 Adverse Event

If the adverse event is deemed not related to IP by the Investigator, dosing with IP may resume at the same dose once the clinical adverse event, which led to suspension of dosing, has resolved or has stabilized.

If the adverse event was deemed to be IP related by the Investigator but not related to PTH < 100 pg/mL (**10.60 pmol/L**), cCa < 7.5 mg/dL (**1.87 mmol/L**) or symptomatic hypocalcemia, dosing with IP may resume once the adverse event has resolved or stabilized **and the central laboratory serum cCa is ≥ 8.3 mg/dL (2.07 mmol/L)** with the dose reduced. For the oral product, the dose should be reduced by 25 mg (if the dose was already at 25 mg, the dose of 25 mg should be resumed). For the IV product, the dose should be reduced by 5 mg or at the minimum dose of 2.5 mg, whichever is greater.

During a hospitalization or when hemodialysis is provided in a location other than the Investigator's site, both oral and IV IPs should be suspended.

6.2.4 Resumption of Investigational Product After Repeated Missed Doses

If more than 14 consecutive days of IP are missed (eg, extended hospitalization for an adverse event unrelated to IP, vacation), a central laboratory cCa must be obtained prior to restarting IP. Only after the **central laboratory** cCa is ≥ 8.3 mg/dL (**2.07 mmol/L**) should dosing with IP resume. Intravenous IP dosing will be restarted by the IVR/IWR at 5 mg and oral IP dose at 25 mg. If the subject's last IV dose was 2.5 mg, then the subject should resume IV dosing at the 2.5 mg dose level.

6.2.5 cCa measured by the local laboratory

A cCa can only be collected and measured by the local laboratory for the management of safety concerns and/or suspension of IP. All cCa results measured by the local laboratory will be recorded on the eCRF. If the cCa is < 7.5 mg/dL (1.87 mmol/L) or the subject experiences symptomatic hypocalcemia, refer to Section 6.2.3.2 for further management. The IP can only be resumed once the cCa measured by the central laboratory is ≥ 8.3 mg/dL (2.07 mmol/L).

A local laboratory cCa and central laboratory cCa must not be collected at the same time.

If the local laboratory cCa is < 7.5 mg/dL (1.87 mmol/L), suspend IP by registering a suspension in IVR/IWR with the reason of adverse event related to IP or symptomatic hypocalcemia depending on the clinical assessment.

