[REDACTED] but maintaining cCa $\geq 8.3 \text{ mg/dL (2.07 mmol/L)}$. Doses of IP will be managed by IVR/IWR and will be based on regular measurements of serum PTH and cCa levels obtained the week before or week of dose adjustment. **Dosing of IP may occur if the cCa results from the central laboratory are not available (as described in Section 6.2.3); however, IV IP dose cannot be resumed or increased without an available cCa result from the central laboratory for the prior or current week.** Dosing with IP may be suspended, and dosing resumed at a lower dose according to protocol-defined rules for low predialysis PTH (based on central laboratory values) or cCa values, for symptomatic hypocalcemia, or for other drug-related adverse events. **Corrected Calcium results from the local laboratory can only be used for the management of safety concerns and for suspension of IP; results must not be used for resumption or titration of IP. A local cCa and central laboratory cCa, must not be collected at the same time.**

For a full list of study procedures, including the timing of each procedure, please refer to **Section 7** and the Schedule of Assessments (**Table 2**). The dosing schema is provided in **Table 3**.

Statistical Considerations: The primary objective of the study is to determine whether etelcalcetide is non-inferior to cinacalcet in achievement of a $> 30\%$ reduction from baseline in mean predialysis PTH during the EAP. Etelcalcetide will be considered non-inferior to cinacalcet if the upper bound of the 2-sided 95% confidence interval (CI) of the treatment difference (cinacalcet – etelcalcetide) is smaller than 12% (see **Section 10.2**). If this criterion is met, the 2 key secondary endpoints will be tested sequentially. The superiority testing for the endpoint of achievement of a $> 50\%$ reduction from baseline in mean predialysis serum PTH during the EAP will be carried out first. Only if the result achieves statistical significance, the secondary endpoint of achievement of a $> 30\%$ reduction from baseline in mean predialysis serum PTH during the

EAP will be tested for superiority. The other secondary endpoints that will formally tests if both key secondary endpoints are statistically significant. To control for the family-wise error rate, the Hochberg procedure of adjustment for multiple comparisons will be used for the testing of the other secondary endpoints.

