6.2.1.2 Dosage Adjustments, Delays, Rules for Withholding or Restarting, Permanent Discontinuation

Sites and subjects will be blinded to central laboratory serum PTH values. Routine local PTH monitoring during the study should be suspended. IP dose titration will be managed by an IVR/IWR and will be based on predialysis serum PTH and cCa results **from the central laboratory** obtained during the prior **or current** week.

Subjects will be treated with IV IP three times weekly at the end of hemodialysis, for 26 weeks. The starting dose of IV IP is 5 mg and will be titrated by the IVR/IWR to target predialysis [REDACTED] and maintain cCa \geq 8.3 mg/dL (2.07 mmol/L). The minimum IV IP dose is 2.5 mg, and the maximum dose is 15 mg.

Each subject's predialysis central laboratory serum PTH and cCa result will be evaluated by the IVR/IWR to determine if the dose of IP should be increased. The dose of IP may be increased by the IVR/IWR during weeks 5, 9, 13, and 17 per [Table 1](#) unless any of the following criteria are met:

- subject has missed 3 or more IV doses during the prior 3 weeks
- the dose of IP was reduced within the prior 3 weeks
- there is an ongoing adverse event, including symptomatic hypocalcemia that precludes a dose increase
- **most recent** predialysis serum cCa < 8.3 mg/dL (2.07 mmol/L) during the prior **or current** week
- **most recent** predialysis [REDACTED] during the prior **or current** week

Table 1. Investigational Product Dosing Algorithm Based on PTH

PTH (pg/mL)	IV IP Dose If Current Dose < 10mg	IV IP Dose If Current Dose 10 mg	IV IP Dose If Current Dose 12.5 mg	Oral IP Dose
PTH > 450 (47.70 pmol/L)	Increase dose by 2.5 mg	Increase dose by 5 mg	Increase dose by 2.5 mg	Increase dose by 25 mg
300 (31.80 pmol/L) < PTH ≤ 450 (47.70 pmol/L)	Increase dose by 2.5 mg	Increase dose by 2.5 mg	Increase dose by 2.5 mg	Increase dose by 25 mg
PTH ≤ 300 (31.80 pmol/L)	Maintain dose	Maintain dose	Maintain dose	Maintain dose
PTH < 100 (10.60 pmol/L)	If 2 consecutive values at least 1 week apart, suspend dose	If 2 consecutive values at least 1 week apart, suspend dose	If 2 consecutive values at least 1 week apart, suspend dose	If 2 consecutive values at least 1 week apart, suspend dose

IP = investigational product; IV = intravenous; PTH = parathyroid hormone

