6.2.3.2 Low Predialysis Serum Corrected Calcium

Administration of etelcalcetide or ingestion of cinacalcet, both potent agonists of the CaR, may result in rapid and sustained suppression of PTH levels.

Management of subjects with rapid and sustained reductions in PTH includes careful monitoring of serum calcium by the Investigator. Supplementation with oral calcium and/or increasing the dialysate calcium concentration may be instituted by the Investigator if serum cCa is below the lower limit of the reference range or there is a rapid large reduction in serum calcium, especially in subjects with PTH > 700 pg/mL (**74.20 pmol/L**) and markedly elevated serum alkaline phosphatase (ALP) at baseline. Increased calcium supplementation may only be needed on a temporary basis until mineral balance is re-established at the reduced PTH level.

The following guidance is provided for the management of serum cCa below the lower limit of the reference range with any change to therapy based on Investigator clinical judgment. If **the cCa measured by either the central or local laboratory is < 8.3 mg/dL (2.07 mmol/L)**, the following options may be taken by the Investigator:

- May increase oral calcium intake
- May increase dialysate calcium concentration
- May initiate or increase active vitamin D analogues if other therapies are ineffective

If **the cCa measured by either the central or local laboratory is < 7.5 mg/dL (1.87 mmol/L)** or the subject experiences symptomatic hypocalcemia, **in addition to the above actions, do the following:**

- Suspend dosing with IP, and at the next hemodialysis session following notification of the low serum calcium result, draw a confirmatory predialysis serum cCa sample **and send to the central laboratory**.
- Obtain weekly predialysis **central laboratory** serum cCa. Once predialysis serum cCa \geq 8.3 mg/dL (**2.07 mmol/L**) and any hypocalcemic symptoms have resolved the IVR/IWR will provide instructions to resume dosing. For the oral IP, the dose should be reduced by 25 mg or at the minimum dose of 25 mg, whichever is greater. For the IV IP, the dose should be reduced by 5 mg or at the minimum dose of 2.5 mg, whichever is greater. Resume routine laboratory monitoring per [Table 2](#), the Schedule of Assessments. Refer to [Section 7.2](#) for central laboratory samples to be submitted.

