9.2.3 Changes in Serum Calcium and Symptomatic Hypocalcemia

Serum cCa levels will be analyzed by the central laboratory throughout the study, and these results will be incorporated in the clinical database. **The cCa measured by the local laboratory and collected for the management of safety concerns will also be incorporated in the clinical database.** Per [Section 6.2.3.2](#) dosing with IP will be suspended if a predialysis serum cCa < 7.5 mg/dL (1.87 mmol/L) value **from either the central or local laboratory** is observed. A repeat **central laboratory** serum cCa will be obtained prior to hemodialysis at the next hemodialysis session, to allow verification of the low serum cCa level. **Central laboratory** serum cCa will continue to be monitored per protocol if IP dosing is suspended for low serum cCa. Dosing may subsequently resume when **central laboratory** serum cCa \geq 8.3 mg/dL (2.07 mmol/L) and any hypocalcemic symptoms have resolved with the dose (1) reduced by 5 mg, or at the minimum dose of 2.5 mg, whichever is greater for IV IP, or (2) reduced by 25 mg, or at the minimum dose of 25 mg, whichever is greater for oral IP.

Investigators should assess subjects for the onset of signs and symptoms associated with low serum calcium (see [Section 6.2.3.3](#)) at each visit. **Any** asymptomatic reductions in serum cCa below 7.5 mg/dL (1.87 mmol/L) **from either the central or**

local laboratory or asymptomatic reductions in serum cCa between 7.5 mg/dL (1.87 mmol/L) and < 8.3 mg/dL (2.07 mmol/L) from either the central or local laboratory that the investigator deems clinically significant (eg, required medical management) should be reported on the eCRF as “blood calcium decreased.”

When signs and symptoms associated with low serum calcium are observed, “hypocalcemia” should be reported as the adverse event and the associated signs and symptoms should also be captured.

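### Section 6.2.4 overlaps with the hypocalcemia restart rule and, read literally, restarts IV IP at 5 mg instead of 2.5 mg from a last dose of 5 or 7.5 mg

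*Protocol*

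**What the plan says.** **Long-gap rule (Protocol 6.2.4).** The trigger begins "If more than 14 consecutive days of IP are missed (eg, extended hospitalization for an adverse event unrelated to IP, vacation"; the reasons are given only as examples. A central cCa of at least 8.3 mg/dL is required, and then "Intravenous IP dosing will be restarted by the IVR/IWR at 5 mg and oral IP dose at 25 mg". The single exception is a last IV dose of 2.5 mg, which resumes at 2.5 mg.

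**Hypocalcemia rule (Protocol 6.2.3.2).** After cCa below 7.5 mg/dL or symptomatic hypocalcemia, IP is suspended until a weekly central cCa reaches 8.3 mg/dL and symptoms have gone. Then: "For the IV IP, the dose should be reduced by 5 mg or at the minimum dose of 2.5 mg, whichever is greater". The oral cut is 25 mg with a floor of 25 mg. No limit is set on the length of the suspension. Section 9.2.3 repeats the rule ("any hypocalcemic symptoms have resolved with the dose (1) reduced by 5 mg, or at the minimum dose of 2.5 mg").

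**Related text.** Section 6.2.3.3: "If dosing with IP is suspended for symptomatic hypocalcemia, dosing may resume at a lower dose once symptomatic hypocalcemia has resolved". Synopsis, Procedures: "Dosing with IP may be suspended, and dosing resumed at a lower dose according to protocol-defined rules". Section 6.2.5 sends the reader to 6.2.3.2 for low cCa or symptomatic hypocalcemia, and for a low local cCa tells the site to "suspend IP by registering a suspension in IVR/IWR with the reason of adverse event related to IP or symptomatic hypocalcemia", depending on the clinical assessment. Sections 6.2.1.2 and 6.2.2.2 point to 6.2.3 and 6.2.4 together for resumption and do not rank them.

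**The concern.** A hypocalcemia suspension that runs past 14 days fits both rules, and at two IV dose levels they give different restart doses. Taken literally, 6.2.4 reverses the intended caution. A subject on 5 or 7.5 mg whose calcium recovers within two weeks restarts at 2.5 mg, while one who takes longer restarts at 5 mg. From 5 mg that is no reduction at all, contrary to 6.2.3.3.

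The stake is safety in the etelcalcetide arm only, because IV IP is placebo in the cinacalcet arm. The IVR/IWR issues the restart instruction, so one rule or the other has to be programmed.

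**Working it through.** **Inputs.** IV doses run from 2.5 to 15 mg (6.2.1.2) and oral doses from 25 to 100 mg (6.2.2.2). The restart rules are those of 6.2.3.2 and 6.2.4. Let d be the last dose in mg.

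**IV formulas.** 6.2.3.2: max(d − 5, 2.5). 6.2.4: 5, or 2.5 if d = 2.5.

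| Last IV dose | 6.2.3.2 | 6.2.4 | Ratio, 6.2.4 to 6.2.3.2 |
|---|---|---|---|
| 2.5 | 2.5 | 2.5 | 1.0 |
| 5 | 2.5 | 5 | 2.0 |
| 7.5 | 2.5 | 5 | 2.0 |
| 10 | 5 | 5 | 1.0 |
| 12.5 | 7.5 | 5 | 0.67 |
| 15 | 10 | 5 | 0.5 |

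So 6.2.4 is higher at 2 of 6 levels, equal at 2 and lower at 2.

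**Oral formulas.** 6.2.3.2: max(d − 25, 25). 6.2.4: 25. For last doses of 25, 50, 75 and 100 mg, 6.2.3.2 gives 25, 25, 50 and 75 mg against 25 mg throughout. 6.2.4 is higher at 0 of 4 levels.

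**Size at the two affected levels.**
- From 5 mg: the cut is 1 − 2.5/5 = 50% under 6.2.3.2 and 1 − 5/5 = 0% under 6.2.4.
- From 7.5 mg: 1 − 2.5/7.5 = 67% against 1 − 5/7.5 = 33%.
- Given three times weekly: 3 × 2.5 = 7.5 mg per week against 3 × 5 = 15 mg per week.

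**Can the overlap occur?** Yes. Calcium has to rise by more than 8.3 − 7.5 = 0.8 mg/dL, and it is checked weekly. Two weekly results still below 8.3 mg/dL bring the gap to about 14 days, and waiting for the next one takes it past that.

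**When does it matter most?** Section 6.2.1.2 states: "The dose of IP may be increased by the IVR/IWR during weeks 5, 9, 13, and 17 per" Table 1. The start is 5 mg and the step below 10 mg is 2.5 mg. The highest scheduled IV dose is therefore 5 mg in weeks 1 to 4 and 5 + 2.5 = 7.5 mg in weeks 5 to 8. For a suspension starting in those weeks, 6.2.4 gives the same dose or double, never a lower one. This rests on the scheduled increases; footnote b of Table 2 also allows changes at any time.

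**How many subjects?** This cannot be derived. Protocol 2.2.1 reports symptomatic hypocalcemia in 5.0% on etelcalcetide and 2.3% on cinacalcet in Study 20120360, but the documents give no suspension lengths.

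**The case against.** The strongest answer is that the rules do not compete, because 6.2.4 is about missed doses and 6.2.3 about suspended ones. Much supports this as the intent:
- Section 6.2.3 names missed and suspended doses separately, and its subsections carry their own resumption rules without time limits.
- Both examples in 6.2.4 are unrelated to IP.
- Section 6.2.5 refers hypocalcemia to 6.2.3.2, and 9.2.3 repeats the reduction whatever the length of the suspension. A specific rule would ordinarily prevail over a general one.
- Scheduled PTH samples are about two weeks apart. If 6.2.4 covered every suspension, it would often displace the low-PTH restart rule in 6.2.3.1, which is implausible.

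A reader might therefore be tempted by a stronger criticism: that the protocol directs a doubled restart dose after any long gap, or gives no guidance on which rule prevails. The documents support neither. The doubling arises only at 5 and 7.5 mg IV, only for hypocalcemia suspensions longer than 14 days, and only on a literal reading. The referral in 6.2.5 is guidance, although it sits under a heading about local cCa.

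What remains is that the wording does not remove the overlap. The list in 6.2.4 is open. Hospitalization is called a suspension in 6.2.3 and is an example of missed IP in 6.2.4, so the two terms are not kept apart. The sponsor wrote the carve-out elsewhere: 6.2.2.1 limits its rule for up to 7 missed oral doses to reasons other than those in Section 6, and SAP 6.3 excludes protocol-specific withholding from its own rule on more than 14 missed days. Section 6.2.4 has no such words.

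**Conclusion.** Wrong as written, as an internal conflict in a dosing rule, but a low-impact safety point that the sponsor should consider. At last IV doses of 5 and 7.5 mg, one of two applicable texts gives twice the restart dose of the other after prolonged hypocalcemia.

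The risk is limited. Both routes require a central cCa of at least 8.3 mg/dL, 5 mg is the dose at which everyone starts, and the dose may be decreased at any time (Tables 2 and 3, footnotes). At 12.5 and 15 mg IV, and at 75 and 100 mg oral, 6.2.4 is the more cautious rule. Few subjects are likely to be affected.

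The conclusion assumes a literal reading of 6.2.4. It does not show that any subject would in fact be restarted at 5 mg, since the IVR/IWR specification is outside the documents. A reader might also look for an effect on the efficacy conclusions; no endpoint definition, alpha or power figure depends on this rule.

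**What to change.** Add to 6.2.4: after a suspension under 6.2.3.2 or 6.2.3.3, the resumption conditions and dose reduction in 6.2.3.2 apply; if the gap also exceeds 14 days, the lower of the two restart doses is used.

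For last IV doses of 2.5, 5, 7.5, 10, 12.5 and 15 mg, the restart doses then become 2.5, 2.5, 2.5, 5, 5 and 5 mg, and oral IP restarts at 25 mg. Compared with 6.2.4 read literally, only the 5 and 7.5 mg IV levels change. Compared with 6.2.3.2 alone, long gaps from 12.5 or 15 mg IV and from 75 or 100 mg oral would restart lower. If the sponsor does not want that, a plain cross-reference making 6.2.3.2 govern also resolves the conflict.

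Confirm that the IVR/IWR applies the rule, including when a local cCa below 7.5 mg/dL has been registered as an IP-related adverse event, since that reason does not by itself identify hypocalcemia.

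The cost is a short amendment and an IVR/IWR check, with no extra data or subjects.

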6.3 Other Protocol-required Therapies

Dialysate calcium must remain ≥ 2.5 mEq/L (1.25 mmol/L) for the duration of the study.

6.4 Hepatotoxicity Stopping and Rechallenge Rules

Subjects with abnormal hepatic laboratory values (ie, ALP, AST, ALT, total bilirubin [TBL]) and/or international normalized ratio (INR) and/or signs/symptoms of hepatitis (as described below) may meet the criteria for withholding or permanent discontinuation of Amgen IP or other protocol-required therapies (as specified in the Guidance for Industry Drug-Induced Liver Injury: Premarketing Clinical Evaluation, July 2009). **Note: If the central laboratory is unable to perform the analysis of the hepatic laboratory tests (as discussed with Amgen during screening) then those tests should be measured by the local laboratory.**

6.4.1 Criteria for Permanent Discontinuation of Amgen Investigational Product and Other Protocol-required Therapies due to Potential Hepatotoxicity

IP should be discontinued permanently by the Investigator and the subject should be followed according to the recommendations in [Appendix A](#) (Additional Safety Assessment Information) for possible drug-induced liver injury (DILI), if ALL of the criteria below are met.

- TBL > 2 x ULN or International Normalized Ratio (INR) > 1.5
- AND increased AST or ALT from the relevant baseline value as specified below:

Baseline AST or ALT value	AST or ALT elevation
< ULN	> 3x ULN

- **AND no other cause for the combination of laboratory abnormalities is immediately apparent; important potential causes for abnormal AST/ALT or TBL values include, but are not limited to:**
 - Obstructive gall bladder or bile duct disease
 - Viral or alcoholic hepatitis (eg, Hepatitis A/B/C/D/E, Epstein-Barr Virus, cytomegalovirus, Herpes Simplex Virus, Varicella, etc)
 - Hypoxic or ischemic hepatopathy or congestive hepatopathy in association with significant right sided heart failure
 - Concomitant administration of other hepatotoxins, including drugs that inhibit bilirubin glucuronidation (eg, indinavir, atazanavir, irinotecan) or herbal or dietary supplements
 - Heritable disorders causing impaired glucuronidation (eg, Gilbert's Syndrome); alpha-one antitrypsin deficiency
 - Autoimmune hepatitis
 - Nonalcoholic Steatohepatitis (NASH) or other “fatty liver disease”

If an alternative cause for hepatotoxicity is identified or less stringent conditions developed than what are noted above, determine (based on subject population and/or

severity of the hepatotoxicity or event) if Amgen IP and other protocol-required therapies should be withheld or permanently discontinued, as deemed appropriate for the safety of the subject.

6.4.2 Criteria for Conditional Withholding of Amgen Investigational Product and Other Protocol-required Therapies due to Potential Hepatotoxicity

For subjects that do not meet the criteria for permanent withholding of IP outlined above, IP should be withheld if ANY of the following criteria are met, and the subject should be evaluated for DILI:

Elevation of either AST or ALT according to the following schedule:

Baseline AST or ALT value	AST or ALT elevation
Any	> 8 x ULN at any time
Any	> 5 x ULN but < 8 x ULN for \geq 2 weeks
Any	> 5 x ULN but < 8 x ULN and unable to adhere to enhanced monitoring schedule

AST = aspartate aminotransferase; ALT = alanine transaminase; ULN = upper limit of normal

- OR: TBL > 3x ULN at any time
- OR: ALP > 8x ULN at any time

If IPs are withheld, the subject is to be followed according to recommendations in [Appendix A](#) for possible DILI. Rechallenge may be considered if an alternative cause for impaired liver tests (ALT, AST, ALP) and/or elevated TBL, is discovered and the laboratory abnormalities resolve to normal or baseline ([Section 6.4.3](#)).

6.4.3 Criteria for Rechallenge of Amgen Investigational Product and Other Protocol-required Therapies After Potential Hepatotoxicity

The decision to rechallenge the subject should be discussed and agreed upon unanimously by the subject, investigator, and Amgen.

If signs or symptoms recur with rechallenge, then IP should be permanently discontinued. Subjects who clearly meet the criteria for permanent discontinuation (as described in [Section 6.4.1](#)) should never be rechallenged.

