4.1.2 Exclusion Criteria

- 201 Currently receiving treatment in another investigational device or drug study, or ≤ 30 days since ending treatment on another investigational device or drug study(s). Other investigational procedures while participating in this study are excluded.
- 202 Subject has received etelcalcetide in a prior clinical trial of etelcalcetide.
- 203 Subject has received cinacalcet during the 3 months prior to the first screening laboratory assessments.
- 204 Subject has known sensitivity to any of the products or components of either cinacalcet or etelcalcetide to be administered during dosing.
- 205 Subject has previously been randomized in this study.
- 206 Anticipated or scheduled parathyroidectomy during the study period.
- 207 Subject has received a parathyroidectomy within 6 months prior to dosing.
- 208 Anticipated or scheduled kidney transplant during the study period.
- 209 Subject has an unstable medical condition based on medical history, physical examination, and routine laboratory tests, or is otherwise unstable in the judgment of the Investigator.
- 210 Malignancy within the last 5 years of screening (except non-melanoma skin cancers or cervical carcinoma in situ).

211 Subject is unwilling or unable to avoid consumption of grapefruit juice during the study period.

212 Subject is pregnant or nursing, or planning to become pregnant or nurse during treatment or within 3 months after the last dose of etelcalcetide or 30 days after the last dose of cinacalcet.

213 Female subject of childbearing potential who is unwilling to use an acceptable method of effective contraception during treatment with investigational product (IP) through 3 months after the last dose of IP. Refer to [Section 6.9](#) for additional information on pregnancy prevention and definition of woman of childbearing potential.

214 Subject has a history of symptomatic ventricular dysrhythmias or Torsades de Pointes.

215 Subject has a history of myocardial infarction, coronary angioplasty, or coronary arterial bypass grafting within the past 6 months prior to screening.

216 Subject has clinically significant abnormalities on prestudy clinical examination or abnormalities on the most recent central laboratory tests during the screening period prior to randomization according to the Investigator including but not limited to the following:

- serum albumin < 3.0 g/dL (**30 g/L**)
- serum magnesium < 1.5 mg/dL (**0.62 mmol/L**)

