- serum transaminase (alanine transaminase [ALT] or serum glutamic pyruvic transaminase [SGPT], aspartate aminotransferase [AST] or serum glutamic oxaloacetic transaminase [SGOT]) > 3 times the upper limit of normal (ULN) at screening

Note: if results of serum transaminases are not available, Amgen should be notified prior to randomization; serum transaminases may be measured at the local laboratory

217 Subject likely not available to complete all protocol-required study visits or procedures, and/or to comply with all required study procedures to the best of the subject and Investigator's knowledge.

218 History or evidence of any other clinically significant disorder, condition or disease (with the exception of those outlined above) that, in the opinion of the Investigator or Amgen physician, if consulted, would pose a risk to subject safety or interfere with the study evaluation, procedures or completion.

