6.2.3 Suspension and Reduction of Oral and Intravenous Investigational Product

Dosing with IP may be temporarily suspended by the Investigator or by the IVR/IWR at any time if ANY of the criteria below apply. IP dosing may resume only after ALL criteria contributing to suspension of IP dosing are resolved.

- two consecutive predialysis central laboratory PTH < 100 pg/mL (**10.60 pmol/L**) at least 1 week apart (see [Section 6.2.3.1](#))
- cCa is < 7.5 mg/dL (**1.87 mmol/L**) (see [Section 6.2.3.2](#) measured by either the central or local laboratory)
- subject experiences symptomatic hypocalcemia (see [Section 6.2.3.3](#))
- there is any other ongoing adverse event that, in the opinion of the Investigator, necessitates suspension of IP dosing

The site will immediately enter the information in IVR/IWR and electronic data capture (EDC) system when a dose suspension rule is invoked and the reason for missed or suspended doses is recorded on the subject eCRF. Even when dosing with IP is suspended per protocol, all scheduled assessments should be completed.

During a hospitalization or when hemodialysis is provided in a location other than the Investigator's site, both oral and IV IPs should be suspended **When hemodialysis is provided in a location other than the Investigator's site, the visit should not be registered in the IVR/IWR. The reasons for missed doses should be recorded on the subject eCRF.**

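### The permanent liver-stop table in Protocol 6.4.1 has no row for subjects whose AST and ALT are both at or above ULN at baseline, which leaves a narrow band with no mandatory stop

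*Protocol*

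**What the plan says.** **Permanent stop (Protocol 6.4.1).** All three criteria must hold: TBL > 2 x ULN or INR > 1.5; a transaminase criterion, "AND increased AST or ALT from the relevant baseline value as specified below"; and no other cause immediately apparent. The table has a single row: baseline < ULN, elevation > 3 x ULN. The Amendment 3 change log prints the same single row in both the replaced and the replacement text, so a row lost in reproduction is unlikely. A closing clause covers cases where another cause is found or "less stringent conditions developed than what are noted above": the site is to decide, by subject population and severity, whether to withhold or stop.

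**Eligibility (4.1.2, criterion 216).** The named transaminase limit is more than "3 times the upper limit of normal (ULN) at screening". The list is "according to the Investigator including but not limited to the following", so lower values may be excluded by judgment but need not be.

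**Withholding (6.4.2).** For subjects short of 6.4.1, "IP should be withheld if ANY of the following criteria are met": AST or ALT > 8 x ULN; > 5 to < 8 x ULN for at least 2 weeks, or when enhanced monitoring cannot be kept; TBL > 3 x ULN; ALP > 8 x ULN. The baseline column of this table reads Any.

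**Rechallenge.** Under 6.4.2, after withholding, it may be considered if an alternative cause is found and values return to normal or baseline. Section 6.4.3 requires unanimous agreement and adds that "Subjects who clearly meet the criteria for permanent discontinuation" in 6.4.1 are never to be rechallenged.

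**General adverse-event route.** Section 6.2.3 allows suspension when "there is any other ongoing adverse event that, in the opinion of the Investigator, necessitates suspension of IP dosing". For an IP-related event, 6.2.3.4 says "dosing with IP may resume once the adverse event has resolved or stabilized", at a reduced dose and with central cCa of at least 8.3 mg/dL. Section 8.3.1 lists an adverse event as a reason for removal from treatment.

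**Appendix A.** Combined AST/ALT and TBL/INR elevation must be reported as an SAE within 24 hours if it meets the Section 6.4 criteria. Close observation starts at AST or ALT > 3 x ULN, with no baseline condition.

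**The concern.** A rule that needs all its criteria, with one criterion tied to a baseline category, cannot be met by anyone outside that category. The reference to a relevant baseline, and the Any entry in the 6.4.2 table, suggest that more than one category was meant to be covered.

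The effect is that identical on-study liver values are handled differently by baseline. A subject with normal baseline enzymes must be stopped for good and reported within 24 hours. A subject with both enzymes raised at baseline may be left to site judgment, in a study planned for about 120 centers. SAP 9.6.3 has no baseline limit in its Hy's law laboratory criteria, so the analysis could list a subject as a potential case whom the stopping rule did not reach.

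**Working it through.** No sample size, power or alpha figure is involved. The check applies the written rules to each baseline that criterion 216 allows.

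**Step 1. Can 6.4.1 be met?**

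| Baseline AST and ALT | Transaminase criterion in 6.4.1 |
|---|---|
| Both < ULN | Can be met, at > 3 x ULN |
| One < ULN, the other ≥ ULN | Can be met through the enzyme that was < ULN |
| Both from ULN to 3 x ULN | No row applies; never met |

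Only the third group is affected.

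**Step 2. Two examples in that group, no other cause apparent.**

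*Example A:* both enzymes 1.5 x ULN at baseline, then ALT 4.5 x ULN, TBL 2.5 x ULN, ALP not raised. Section 6.4.1 is not met, for lack of a row. Nor is 6.4.2: 4.5 is not > 5, 2.5 is not > 3, and ALP is not > 8 x ULN.

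*Example B:* ALT 7 x ULN for under 2 weeks with monitoring kept, TBL 2.5 x ULN, ALP ≤ 8 x ULN. With a normal baseline, 6.4.1 is met (2.5 > 2 and 7 > 3). With both enzymes raised at baseline it is not. Nor is 6.4.2: 7 is not > 8, the duration is under 2 weeks, and 2.5 is not > 3. The SAP Hy's law criteria are met at any baseline if ALP is < 2 x ULN within 7 days (7 > 3 and 2.5 ≥ 2).

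**Step 3. The full band.** Take the 6.4.1 thresholds and remove everything that 6.4.2 catches. No liver rule directs stopping or withholding when all of these hold:
- TBL > 2 to 3 x ULN, or INR > 1.5 with TBL ≤ 3 x ULN;
- AST or ALT > 3 to 5 x ULN, or > 5 to < 8 x ULN for under 2 weeks with monitoring kept;
- ALP ≤ 8 x ULN;
- no other cause apparent.

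**Step 4. When the rule can act.** Tables 2 and 3 schedule chemistry at screening, early termination and the 30-day follow-up. Both post-baseline visits come after the last dose (7.2.4, 7.2.5), and INR is not among the analytes printed in Table 4. During treatment the rule therefore acts only on unscheduled tests. The Appendix A report can still depend on the 6.4 criteria for chemistry drawn at those two visits.

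**Step 5. The proposed row.** Threshold in multiples of ULN = max(3, k x baseline), with k = 2 assumed.

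| Baseline (x ULN) | Threshold at k = 2 |
|---|---|
| 1.0 to 1.5 | 3 |
| 2.0 | 4 |
| 2.9 | 5.8 |
| 3.0 | 6 |

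Example A is caught (4.5 > 3), and so is example B at every eligible raised baseline (7 > 6). A move from 2.9 to 3.1 x ULN is not caught (3.1/2.9 = 1.07, below 2).

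Range for k at baseline 3.0: 1.5 gives 4.5, 2.5 gives 7.5, 3 gives 9. Keeping 3k ≤ 8, the 6.4.2 limit, needs k ≤ 8/3, about 2.67.

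**The case against.** The strongest reply is that the band already has an owner. The closing clause of 6.4.1 directs a decision and leaves only its outcome to judgment; subject population can reasonably include people with raised baseline enzymes. Judgment is defensible here, because a flat > 3 x ULN rule would permanently stop a trivial rise from 2.9 to 3.1 x ULN. Example B is also short-lived: withholding becomes mandatory at 2 weeks, or sooner if monitoring fails, ALT passes 8 x ULN or TBL passes 3 x ULN. Meanwhile Appendix A requires repeat tests within 24 hours, daily retesting at TBL > 2 x ULN or INR > 1.5, a cause work-up and a hepatology consult. Criteria 209, 216 and 218 let investigators exclude some of these subjects, and known viral hepatitis or fatty liver disease would fail the third 6.4.1 criterion anyway. Section 6.4 also cites a liver-injury guidance that is not available here, so whether it calls for such a row cannot be checked.

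Most of this stands and limits the consequence. It does not make 6.4.1 satisfiable for these subjects, and close observation does not itself direct stopping.

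A reader might infer that these subjects cannot be stopped at all, or that losing the 6.4.3 bar leaves them open to rechallenge at any severity. The documents support neither. Suspension and removal for an adverse event remain open. Once 6.4.2 withholding applies, rechallenge already needs an alternative cause, recovery to normal or baseline, and unanimous agreement, so the bar adds little there.

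**Conclusion.** The gap is real and minor. An eligible subject with both AST and ALT from ULN to 3 x ULN at baseline cannot meet the 6.4.1 stop. In the band set out above, no liver rule directs stopping or withholding, and the automatic 24-hour SAE report is not triggered. In that band such an event becomes an SAE only through the general definition in 9.1.2, which does name drug-induced liver injury as an example of a medically important event.

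The size cannot be given as a number. The documents do not say how many subjects would have both enzymes raised at baseline, and the on-study band is narrow. The conclusion rests on reading the single-row table as complete and on reading the Appendix A reference to 6.4 as meaning its numerical criteria.

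It would be wrong to extend the point to subjects with only one raised enzyme, who can still qualify through the other. It does not touch the sample size, the multiplicity scheme or the efficacy conclusions.

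**What to change.** Add one row to the 6.4.1 table: for baseline ≥ ULN, AST or ALT > 3 x ULN and > 2 x the subject's own baseline. The multiple of 2 is an assumption, not taken from the documents. The sponsor's safety function should confirm it, and at most about 2.67 keeps the threshold at or below 8 x ULN. Use the baseline in SAP 5.2, the last non-missing value on or before Study Day 1, so no new test is needed. The 6.4.3 bar and the Appendix A report then follow through their existing references to Section 6.4.

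The cost is a protocol amendment with investigator agreement and IRB/IEC approval (12.1) across the planned centers. A few subjects with raised baseline enzymes would also be stopped permanently who could now continue by judgment.
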